- b) Subjects who have no tumor assessment after randomization will have PFS censored at the date of randomization, unless they died before the second scheduled tumor assessment.

Further details and other cases will be described in the statistical analysis plan (SAP).

Analysis of Secondary Endpoints

The secondary endpoints (OS, ORR, and DoR) will be analyzed using the investigator and independent radiological review assessments. The degree of agreement between the investigator and the independent assessment of responses will also be summarized and presented in a table.

The first secondary analysis will compare the OS between the 2 treatment arms by using stratified Log-rank test and the stratification factors included in the primary analysis. An interim OS analysis will be carried out at the time of the Final PFS analysis.

Duration of response (DoR) will be analyzed using the same method as for the progression-free survival.

The proportion of subjects achieving confirmed ORR (complete response [CR]+partial response [PR]) will be summarized and presented by treatment arms and cycle and will be compared between the two treatment arms using Cochran-Mantel-Haenszel (CMH) test with the same stratification factors used for the PFS analysis.

Exploratory Analyses

In order to evaluate if the timing of post-baseline radiological scan influenced the primary outcome, the time from randomization to post-radiological scan will be calculated and an exploratory analyses will be conducted. Means and standard deviation of radiological scan time will be presented by treatment arms and cycle time. Log-rank test will be used to test if cumulative percentages (survival curves) are equal (median time to each cycle from randomization) by treatment arms.

Subgroup Analyses

PFS subgroup analyses by gender, race, and age (< 65 years and \geq 65 years) will be carried out using separate unadjusted Log-rank test for the ITT population.

Definition of Efficacy Endpoints

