Progression-Free Survival (PFS) is defined as the time from randomization to first documentation of objective tumor progression (progressive disease [PD], radiological) according to RECIST (Version 1.1) or death due to any reasons whichever comes first. PFS data will be censored on the day following the date of last tumor assessment documenting absence of PD for subjects who do not have objective tumor progression and are still on study at the time of the analysis, are given anti-tumor treatment other than the study treatment, or are moved from treatment follow-up prior to documentation of objective tumor progression. Subjects having no tumor assessments after randomization who are not known to have died will have PFS censored on the date of randomization.

Overall survival (OS) is defined as the time from the date of randomization to date of death due to any cause. In the absence of confirmation of death, survival time will be censored at the last date the subject is known to be alive. Subjects lacking data beyond randomization will have their survival times censored on the date of randomization.

Overall response rate (ORR) is defined as the proportion of subjects with confirmed CR or confirmed PR according to RECIST (Version 1.1), relative to the total population of randomized subjects. Confirmed responses are those that persist on repeat imaging study at least 4 weeks after the initial documentation of response.

Duration of response (DoR) is defined as the time from the first documentation of objective tumor response to the first documentation of objective tumor progression or to death due to any cause. DoR data will be censored on the day following the date of the last tumor assessment documenting absence of PD for subjects who do not have tumor progression and are still on the study at the time of an analysis, are given antitumor treatment other than the study treatment, are removed from the study follow-up prior to documentation of objective tumor progression, died of non-cancer related cause, including death due to unknown cause in the absence of documented disease progression. **DoR will only be calculated for the subgroup of subjects with an objective tumor response (PR or CR).**

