3.2 Efficacy and Safety Variables

3.2.1 Efficacy Variables

Tumor response will be assessed using RECIST v1.1 criteria. Subjects will undergo assessments at screening and every 8 weeks following Cycle 1, Day 1 until radiological disease progression is documented and confirmed by independent radiology review. Evaluable subjects are those who receive at least 2 cycles of study drug.

Best overall response (BOR) is determined once all assessments from randomization until disease progression or death are recorded. In general, it is the best response across all assessments; however, confirmation of complete response (CR), partial response (PR), and stable disease (SD) will also be used in BOR determination. To confirm CR or PR changes in tumor measurements must be confirmed by repeat assessments that should be no less than 4 weeks (28 days) after the criteria for response are first met. To confirm SD, it must have occurred at least 8 weeks from Cycle 1, Day 1; otherwise, BOR will depend on subsequent assessments.

All subjects will be followed until death from any cause (unless the subject is lost to follow-up, withdraws consent for the entire study, or the sponsor terminates the study early). After the 30-Day Follow-up visit, subjects will be contacted once every 3 months by the site to collect long-term survival data. For subjects with ongoing objective response or disease stabilization at the time of treatment discontinuation, or for subjects who discontinue for reasons other than radiological evidence of progressive disease, tumor assessments will continue to be collected every 2 months during the first year (beginning from the date of the last scan performed prior to treatment discontinuation), every 3 months during the second year, and every 6 months thereafter until disease progression is confirmed by independent radiology review or the start of another anti-tumor therapy that includes anti-cancer surgery/procedure, anti-cancer radiotherapy, and anti-cancer systemic therapy.

Primary Efficacy Endpoint

PFS is defined as the time from randomization date to the first date of radiological PD or death date (due to any reason), whichever event is earlier. PFS in months will be calculated as: (first event date – randomization date + 1) * (12/365.25). Censoring will occur as follows:

- If there are no tumor assessments after randomization, PFS will be censored on the date of randomization.

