- If a subject is known to be alive and progression-free, PFS will be censored on the day of the last tumor assessment.
- If a subject is given anti-tumor treatment (anti-cancer surgery/procedure, anticancer radiotherapy, and anti-cancer systemic therapy other than the study treatment) prior to PD or death, PFS will be censored on the date of the last tumor assessment prior to the start date of the anti-tumor treatment.
- If treatment follow-up ceases prior to objective PD, PFS will be censored on the date of the last tumor assessment.

Secondary Efficacy Endpoints

OS is defined as the time from the date of randomization to the date of death (due to any reason). OS in months will be calculated as: (death date – randomization date + 1) * (12/365.25). Censoring will occur as follows:

- If there are no tumor assessments after randomization, OS will be censored on the date of randomization.
- If there is no confirmation of death, OS will be censored on the date the subject is last known to be alive.

ORR is defined as the proportion of subjects with best overall response (BOR) of confirmed CR or confirmed PR [i.e. objective response (OR)], according to the RECIST 1.1 among subjects with measurable disease at baseline.

DoR is defined as the time from the first date of OR to first date of radiological PD. This will only apply to subjects with confirmed CR or confirmed PR and will be calculated as: (first event date – first OR date + 1) * (12/365.25). Censoring will occur as follows:

- If a subject is known to be alive and progression-free, DoR will be censored on the day following the date of the last tumor assessment.
- If a subject dies of a cause known to be non-cancer related, DoR will be censored on the date of the last progression-free tumor assessment.
- If a subject dies of an unknown cause in the absence of documented PD, DoR will be censored on the date of the last tumor assessment.
- If a subject is given anti-tumor treatment (anti-cancer surgery/procedure, anticancer radiotherapy, and anti-cancer systemic therapy other than the study

treatment) prior to PD or death, DoR will be censored on the date of the last progression-free tumor assessment prior to the start date of the anti-tumor treatment.

• If treatment follow-up ceases prior to objective PD, DoR will be censored on the date of last progression-free tumor assessment.

Tertiary Efficacy Endpoint

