4.7.2 Primary Efficacy Variable – PFS

Primary Analysis on PFS

The primary variable for the assessment of efficacy is PFS, as defined in Section 3.2.1 of this SAP.

PFS based on IRR will be summarized for the ITT population using the Kaplan-Meier method. These summaries will include 1- and 2-year survival probabilities along with corresponding 95% CIs. Graphical displays (i.e. K-M plots), where appropriate, will also be produced.

Median event times and corresponding two-sided 95% CIs for the medians will be provided for PFS. A stratified log-rank test (one-sided, α =0.025) as well as hazard ratios and corresponding 95% CIs from a stratified Cox proportional hazard model, both adjusting for IMDC risk category and prior therapy, will be used to compare PFS between the two treatment arms.

When determining PFS, the recorded date of progression (defined as first time at which progression can be declared) will be used. For progression due to the presence of a new lesion, the date of progression is the first date that the new lesion was observed. If multiple assessments based on the sum of target lesion measurements are done at different times, the date of progression is the date of the last observation or radiological assessment of target lesions that shows a predefined increase in the sum of the target lesion measurements.

The robustness of the study results to the choice of baseline covariates will be investigated as described in Section 4.7.1.2. In addition, the homogeneity of the treatment effect for important subgroups will be investigated as described in Section 4.7.1.6.

A by-subject listing of the primary efficacy data will be provided.

Sensitivity Analyses on PFS

Sensitivity Analysis #1 will be done using the investigator assessment of response, adding in as events any clinical PDs specified by the investigator. A clinical PD is defined to be treatment failure not meeting the criteria for progressive disease but considered by the investigator to require removal of the subject from the study. This analysis will be conducted using the ITT and PP populations.

Sensitivity Analysis #2 will consider the initiation of new anti-tumor treatment to be an event. In this analysis, any death or PD will also be events, even those that occur after two or more missed tumor assessments. This analysis will be conducted using only the ITT population.

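### Read literally, the SAP's fourth PFS censoring rule censors deaths that its own PFS definition counts as events

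*SAP*

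**What the plan says.** SAP 3.2.1 runs PFS from randomization to "the first date of radiological PD or death date (due to any reason), whichever event is earlier". Protocol 14.3.4 also makes death from any cause a PFS event. Neither limits the time between the last scan and the death.

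SAP 3.2.1 then lists four censoring rules for PFS:

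1. "If there are no tumor assessments after randomization, PFS will be censored on the date of randomization".
2. A subject known to be alive and progression-free is censored at the last tumor assessment.
3. A subject given new anti-tumor treatment before PD or death is censored at the last assessment before that treatment.
4. "If treatment follow-up ceases prior to objective PD, PFS will be censored on the date of the last tumor assessment".

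Rule 3 names death; rule 4 does not. The SAP does not define when treatment follow-up ceases, and it does not rank the definition against the rules.

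SAP 4.7.2 describes Sensitivity Analysis #2 as making new anti-tumor treatment an event and adds: "In this analysis, any death or PD will also be events, even those that occur after two or more missed tumor assessments".

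For subjects with no scan after randomization, Protocol 14.3.4 has two wordings. The missing-data steps censor at randomization "unless they died before the second scheduled tumor assessment". The endpoint definition says: "Subjects having no tumor assessments after randomization who are not known to have died will have PFS censored on the date of randomization".

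**The concern.** Protocol 11.1 (item 6) lets a subject leave treatment for clinical progression that does not meet RECIST criteria. Protocol 7.2.4 waives independent verification of PD when there is significant clinical deterioration. Some of these subjects will have no further scan. Survival follow-up continues until death, so their deaths will be in the database.

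Two programmers could each follow the SAP and derive different primary event status, event times, event counts and hazard ratios. If rule 4 is applied as written, deaths are dropped in a group whose prognosis is probably poor, so the censoring may be informative. The trial is open-label, so scan stopping could also differ by arm. The 242-event target at the data cut-off (SAP 4.10) itself depends on which deaths count.

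**Working it through.** **Step 1: one hypothetical subject.** Last scan at week 8 with stable disease; treatment stopped for clinical deterioration; no new therapy; no further scan.

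| Reading | Death at week 20 | Death at week 30 |
|---|---|---|
| PFS definition | Event, week 20 | Event, week 30 |
| Rule 4, literal | Censored, week 8 | Censored, week 8 |
| Rule implied by Sensitivity Analysis #2 | Event (one assessment missed) | Not counted (two missed) |

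The first two rows come from explicit text. The third is only inferred from the contrast drawn in SAP 4.7.2.

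Confining rule 4 to subjects with no death is possible, but the text does not do so. Rule 2 is limited to subjects known to be alive, and rule 4 has no such limit.

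**Step 2: the plan's own figure.** Inputs from SAP 4.9: medians 4 and 6 months (HR = 4/6 = 0.667), 1:1 allocation, one-sided 0.025, 90% power. Schoenfeld:

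events = 4 × (1.960 + 1.282)² / (ln 0.667)² = 4 × 10.507 / 0.1644 = 255.7, which rounds up to 256. The SAP states 255, so the figure reproduces.

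Power = Φ(√d/2 × 0.4055 − 1.960):

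- d = 255: Φ(1.277) = 89.9%
- d = 242: Φ(1.194) = 88.4%

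**Step 3: how far the readings can differ.** The documents do not say how many subjects stop scans before PD and later die, so the rate is an assumption. The simulation used:

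- 161 subjects per arm and exponential times;
- median PFS 4 and 6 months, median OS 12 and 16 months (SAP 4.9);
- uniform accrual over 15 months, cut-off at month 28, scans every 8 weeks;
- a given share of subjects stopping scans at a random time in the first 6 months, unrelated to prognosis;
- an unstratified log-rank test and 300 runs per setting, with all readings applied to the same data.

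Some subjects stop before their first scan, so rules 1 and 4 are covered together. The columns give mean values for: death always an event / always censored / an event only within two scan intervals of the last scan.

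| Stopping, sorafenib / tivozanib | Deaths affected | Events | HR | Disagree on significance |
|---|---|---|---|---|
| 3% / 3% | 4.0 | 294.8 / 290.8 / 291.7 | 0.655 / 0.651 / 0.651 | 3.0% |
| 10% / 10% | 13.4 | 289.8 / 276.4 / 279.2 | 0.665 / 0.654 / 0.656 | 2.0% |
| 20% / 20% | 27.2 | 283.0 / 255.8 / 262.0 | 0.676 / 0.653 / 0.656 | 6.0% |
| 20% / 10% | 20.4 | 286.4 / 265.9 / 270.8 | 0.678 / 0.655 / 0.650 | 4.3% |
| 10% / 20% | 20.3 | 285.9 / 265.6 / 270.1 | 0.666 / 0.656 / 0.665 | 4.3% |

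The largest gap in events is 283.0 − 255.8 = 27.2; the smallest is 294.8 − 290.8 = 4.0. With equal stopping the HR gap runs from 0.004 to 0.023. The 0.028 (0.678 − 0.650) comes from the 20% / 10% row. With 300 runs the disagreement rates carry a standard error of about 1 point (√(0.04 × 0.96/300) = 1.1%).

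For scale, the change from 255 to 242 events recorded in SAP 4.10 is 13 events, about the gap at 10% stopping.

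Simulated totals exceed the trial's target, so only differences between readings are informative.

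**Step 4: informative stopping.** A second set of simulations had subjects stop scans at clinical deterioration and die on average 4 months later. Power is for censor all / count all / two-missed rule.

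| Stopping, sorafenib / tivozanib | Power |
|---|---|
| 3% / 3% | 93.2% / 93.6% / 93.3% |
| 10% / 10% | 90.7% / 93.2% / 92.5% |
| 15% / 8% | 78% / 90% / 89% |
| 8% / 15% | 97% / 94% / 95% |

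With 8% / 15% and no true difference, one-sided rejection was 8.7% / 4.0% / 4.3% against a nominal 2.5%. The imbalance drives the effect, and its sign decides the direction.

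**The case against.** The best defense is that the definition governs. Censoring rules ordinarily apply to subjects without an event, so rule 4 would reach only those whose follow-up ended with no event recorded. The DoR list in SAP 3.2.1 gives some support: it has the same end-of-follow-up rule and also separate rules censoring certain deaths, which suggests that the authors wrote death-censoring where they wanted it. The support is limited, because the SAP's DoR definition does not list death as an event.

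The affected group is also kept small. An End-of-Treatment scan is required unless a recent one showed confirmed PD, and scanning continues after discontinuation without PD. Sensitivity Analysis #1 counts clinical PD as called by the investigator, and #3 counts discontinuation of therapy.

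Most of this stands as evidence of intent and as a limit on size. It does not settle the primary derivation: the SAP nowhere says the definition overrides, and rule 3 names death where rule 4 does not. Sensitivity Analysis #2 cannot isolate the question, because it also makes new treatment an event.

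A reader might infer three stronger points that the documents do not support:

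- **The SAP prescribes three conflicting answers.** Only two are explicit. The missed-assessment answer is an inference, and the wording in SAP 4.7.2 could be mere emphasis.
- **The ambiguity costs about 10 points of power.** That needs an imbalance such as 15% against 8%, which the documents do not give. The only loss figure is 3% dropout per arm, a different quantity. Swapping the imbalance reverses the direction.
- **The remedy is a two-missed-assessment rule in the primary analysis.** It would newly censor PD and deaths that the definition counts. It would clash with rule 3 for a subject who starts new therapy and dies soon after. It also has no fixed window: off-treatment scans become 3-monthly and then 6-monthly, so two missed scans can span about a year.

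**Conclusion.** The concern holds in this form: rule 4, as written, contradicts the endpoint definition for deaths without PD after scan follow-up ends, and the SAP gives no order of precedence. This is a stated rule that yields a wrong result if followed literally. Sensitivity Analysis #2 adds a second gap by implying a primary-analysis rule that does not exist.

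Under the assumptions in step 3 the effect is small at 3% stopping and modest at 10% to 20%. Whether the trial's conclusion would change cannot be determined from the documents. Counting every such death has its own cost: a death found long after the last scan adds unobserved progression-free time. That is a reason for a separate sensitivity analysis, not for leaving the primary rule open.

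**What to change.** 1. In SAP 3.2.1, add *or death* after *objective PD* in the fourth PFS rule. State that a death without prior PD and without prior new anti-tumor treatment is an event on the death date.
2. Give the first rule (no scan after randomization) an exception for death. Reconcile it with the two wordings in Protocol 14.3.4, which differ on whether the exception stops at the second scheduled assessment.
3. State that the primary analysis has no missed-assessment censoring, and remove the implied contrast from Sensitivity Analysis #2. If wanted, report censoring of PD or death after two or more missed assessments as a separate sensitivity analysis, naming the scan schedule that defines a missed assessment.

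Settle these before anyone sees results by arm. The cost is SAP wording and one derivation, with no new data.

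### The protocol and SAP give duration of response several conflicting end events, and the SAP has no explicit rule for a responder who dies of RCC without a progression scan

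*SAP*

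**What the plan says.** **SAP 3.2.1 (secondary endpoints).** "DoR is defined as the time from the first date of OR to first date of radiological PD". Among the censoring rules that follow:
- "If a subject dies of a cause known to be non-cancer related, DoR will be censored" (at the last progression-free assessment).
- "If a subject dies of an unknown cause in the absence of documented PD, DoR will be censored" (at the last assessment).
- For new anti-tumor treatment given "prior to PD or death, DoR will be censored on the date of the last progression-free tumor assessment" before that treatment.
- "If treatment follow-up ceases prior to objective PD, DoR will be censored".

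**Protocol 14.3.4 (definitions of endpoints).** DoR runs from first response "to the first documentation of objective tumor progression or to death due to any cause". The next sentence lists as censored those who "died of non-cancer related cause, including death due to unknown cause in the absence of documented disease progression".

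**Elsewhere in the protocol.** Section 7.1 (disease/response assessment), section 9.1 and Appendix A (1.6.1) each end response at observed or documented progression and do not mention death.

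**For comparison.** The SAP ends PFS at the "first date of radiological PD or death date (due to any reason), whichever event is earlier". Protocol 14.3.4 says that DoR is analysed by the same method as PFS. SAP 4.10 records an update to the best overall response criteria and nothing about DoR.

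**The concern.** Two programmers could code the same responder differently, and each could point to plan text in support. The critical case is a confirmed responder who dies of RCC before any scan shows progression. Protocol 7.2.4 and 11.1 foresee the route, because treatment may stop for clinical deterioration without radiological verification. Under the SAP's sentence on the end event, this death is not an event. Under protocol 14.3.4, it is.

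For a non-cancer or unknown-cause death, protocol 14.3.4 gives both answers: an event under its opening words, censored under the next sentence.

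The choice affects what is reported. A Kaplan-Meier analysis treats a censored responder as someone whose response could have continued, so censoring deaths tends to lengthen DoR. Comparing DoR is a stated secondary objective, and SAP 4.7.3 summarises it in the same way as OS, with 1- and 2-year probabilities. With few responders, recoding one or two deaths can visibly move the curve. The coding should therefore be settled before anyone sees which deaths matter.

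**Working it through.** The documents give no DoR event count, median or death share, so there is no stated figure to reproduce. The check compares the texts, then gives an illustration under stated assumptions.

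**1. How each passage codes a responder's death without a progression scan**

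| Source | RCC death | Non-cancer or unknown cause |
|---|---|---|
| Protocol 14.3.4, opening words | event | event |
| Protocol 14.3.4, censoring sentence | event | censored |
| SAP 3.2.1, end-event sentence alone | not an event | not an event |
| SAP 3.2.1, censoring list | not stated | censored |
| Protocol 7.1, 9.1, Appendix A 1.6.1 | no death component | no death component |
| SAP 3.2.1, PFS | event | event |

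Two versions can be programmed from the SAP. In the *cause-restricted* version an RCC death is an event and other deaths are censored. In the *PD-only* version every death is censored.

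**2. Effect on the median, relative to PD or death from any cause**

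Assumptions, none from the documents: constant hazards; f = share of PD-or-death endings that are deaths without documented PD, 5-20%; c = share of those deaths due to RCC, 30-80%.

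- Cause-restricted: ratio of medians = 1/(1 - f(1 - c))
- PD-only: ratio = 1/(1 - f)

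| f | cause-restricted, c = 0.8 | c = 0.5 | c = 0.3 | PD-only |
|---|---|---|---|---|
| 5% | 1.010 | 1.026 | 1.036 | 1.053 |
| 10% | 1.020 | 1.053 | 1.075 | 1.111 |
| 20% | 1.042 | 1.111 | 1.163 | 1.250 |

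The median rises by about 1-16% (cause-restricted) or 5-25% (PD-only). The two versions differ by (1 - f(1 - c))/(1 - f), which runs from 0.965/0.95 = 1.016 to 0.96/0.80 = 1.200.

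**3. Effect on the 12-month probability**

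With all-cause median m (assumed 9 or 12 months) and median ratio r, S(12) = 0.5^(12/(m·r)).

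- m = 12: all-cause 0.500; cause-restricted 0.503-0.551; PD-only 0.518-0.574.
- m = 9: all-cause 0.397; cause-restricted 0.401-0.452; PD-only 0.416-0.477.

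The shifts are about 0.3-5.5 points and 1.8-8.1 points. A simulation of 200,000 responders with 8-weekly scans and deaths censored at the last scan agrees. At m = 9, f = 20%, c = 0.5 it gave 0.421, 0.459 and 0.501 (any death, cause-restricted, PD-only), shifts of 3.8 and 8.0 points.

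**4. Scale against sampling error**

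At assumed response rates of 8% and 18%, 161 subjects per arm give about 13 and 29 responders. Near S = 0.397 the standard error is roughly √(0.397 × 0.603/n):
- n = 13: 13.6 points
- n = 29: 9.1 points

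The largest shift, 8.1 points, is below one standard error in either case. Simulated trials with 15 months' accrual and a cut-off at 28 months gave 8.0-9.4 endings among 13 responders and 17.8-20.8 among 29. At f = 5-20% that is about 0.4-1.9 and 0.9-4.2 deaths without progression. With half of them from RCC, 0.2-0.95 and 0.45-2.1 deaths depend on the missing rule. The Poisson chance that none occurs is e^(-0.95) to e^(-0.2) = 39-82%, and e^(-2.1) to e^(-0.45) = 12-64%.

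**The case against.** **The two documents agree on which deaths to censor.** This stands. Both censor non-cancer and unknown-cause deaths, so a reader who infers that the SAP departed from the protocol here would be wrong. It also follows that DoR is overstated only relative to PD-or-death, and that cause-restricted DoR is a choice a trial could make. What does not stand is treating the matter as mere preference. Protocol 14.3.4 states an any-cause event and a cause-based exclusion in one paragraph, and both cannot be applied.

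**The SAP's meaning can be worked out.** Largely fair. Naming two kinds of death as censored would be pointless if all deaths were censored, and the DoR formula refers to a generic first event date. The natural reading makes an RCC death an event, which leaves no difference from protocol 14.3.4 on events. The follow-up bullet also appears in the PFS list, where death is an event, so it is weak evidence for censoring. A reader might infer that the SAP drops all deaths, but the text does not establish that. Still, the sentence that defines the endpoint names progression alone, and the natural reading has to be inferred.

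**SAP 4.10 hides no change.** Fair. Under the natural reading no event rule changed, and the progression-only wording matches protocol 7.1, 9.1 and Appendix A. The gap is that 4.10 leaves the competing definitions unaddressed.

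**The trial is open-label, so cause attribution could favour one arm.** A reader might infer this, since the protocol and SAP describe no blinded adjudication of cause of death. Nothing in them shows attribution differing by arm, so no between-arm bias is claimed. Nor is the shift certain in every dataset: censoring a death back at an earlier scan can occasionally lower an estimate. The direction holds in expectation.

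**Conclusion.** The point holds as a conflict of definitions that should be resolved. Protocol 14.3.4 contradicts itself, the SAP names progression as the only end event without saying how to code an RCC death lacking a progression scan, and three other protocol passages omit death.

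On the assumed ranges, the median is longer than under PD-or-death by about 1-16% (protocol 14.3.4's censoring, or the natural reading of the SAP) or 5-25% (all deaths censored). The death shares and response rates are assumptions; constant hazards underlie the formulas.

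The consequence is modest. SAP 4.7.1.4 treats secondary endpoints as supportive, responders are likely to be few, and the shift is within one arm's sampling error. The primary PFS analysis already counts any death and is untouched. The case rests on removing a coding choice before results are known.

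**What to change.** Before the analysis is run:

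1. In protocol 14.3.4 and SAP 3.2.1, define the DoR event once as the first of radiological progression or death from any cause. This is the protocol's own opening wording and matches the PFS event.
2. Remove the cause-of-death censoring from both.
3. Make protocol 7.1, 9.1 and Appendix A 1.6.1 refer to that definition for the DoR analysis. Editing only the two main passages would leave these three in conflict.
4. Keep the cause-restricted version as a labelled sensitivity analysis, stating how an RCC death without a progression scan is coded.
5. Record the change and its reason in SAP 4.10.

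A minor alignment for the same edit: SAP 3.2.1 limits the ORR denominator to subjects with measurable disease, while protocol 14.3.4 uses all randomized subjects and SAP 4.4 and 4.7.3 use ITT. Measurable disease is an entry criterion, so little should change.

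**Cost.** Wording and a censoring flag, with no new data. DoR may look slightly shorter and is no longer a pure progression measure. A specified rule also changes late in an open-label trial, around the 4 October 2018 cut-off, so the dated log entry is essential.
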